### 10.5.4 Investigator's Global Assessment

Investigator's Global Assessment (IGA) score on the target wound is obtained at baseline and post-baseline visits as outlined in the schedule of events. IGA scores will be evaluated at baseline and for post-baseline visits, using a paired t-test for each KB103 target wound vs. control wound.

### 10.5.5 Patient Reported Outcome

Patient reported outcome (PRO) in terms of pain and severity of the target wound is obtained at baseline and post-baseline visits as outlined in the schedule of events, using Wong-Baker Faces Pain Rating scale. Change in the pain ratings will be evaluated at baseline and at post-baseline visits, using a paired t-test for each KB103 target wound vs. control wound.

## 10.6 Safety Analyses

All continuous parameters are summarized using standard summary statistics as appropriate (n, mean, standard deviation (SD), median, minimum, maximum, 25th percentile, and 75th percentile). Summary statistics for categorical variables include frequency counts and percentages.

Patient demographics and relevant baseline data is analyzed descriptively. Inclusion and exclusion criteria ensure that participants are suitable for the study. Premature termination data is tabulated and summarized.

### 10.6.1 Adverse Events

Adverse events are coded using the MedDRA adverse event dictionary. Safety evaluations are based on occurred adverse events, laboratory values, vital signs and appearance of collagen VII antibodies, and RCV. Severities of toxicities is described using the NCI Common Toxicity Criteria (CTC) grades.

Adverse events are grouped into pre-treatment adverse events and treatment-emergent adverse events and are tabulated by preferred terminology and by body system for each study phase. The number of adverse event entries, as well as the number of patients are reported. Analyses include tabulation of adverse event type, relationship to KB103, seriousness, and severity of adverse events according to CTCAE.

### 10.6.2 Physical Examinations

Physical examinations at screening and subsequent follow-up visits are displayed in tabular format displaying number of subjects examined and number and percentage of subjects with abnormalities by physical examination category.

### 10.6.3 Vital Signs

Vital signs are listed and summarized by mean and SD.

### 10.6.4 Laboratory Tests

Laboratory test values are presented in shift tables and by display of changes to baseline. Evaluations of collagen VII antibodies and RCV will be done descriptively.

## 10.7 Handling of Missing and Incomplete Data

For efficacy evaluation, the treatment endpoint is defined as one assessment time point, which includes the last measurement obtained during the study for a variable. No other imputation of values for missing data is performed. Standard clinical monitoring and data management practices are used to ensure the integrity of data.

# 11 Regulatory Obligations

## 11.1 Informed Consent

Before a subject's participation in the trial, the investigator (or designee) is responsible for obtaining written informed consent from the subject or legally acceptable representative (see note below) after adequate explanation of the aims, methods, anticipated benefits, and potential hazards of the study and before any protocol-specific screening procedures or any investigational products are administered. A legally acceptable representative is an individual or other body authorized under applicable law to consent, on behalf of a prospective subject, to the subject's participation in the clinical trial.

The acquisition of informed consent should be documented in the subject's medical records, and the informed consent form should be signed and personally dated by the subject or a legally acceptable representative and by the person who conducted the informed consent discussion (not necessarily an investigator). The original signed informed consent form must be retained in accordance with institutional policy, and a copy of the signed consent form must be provided to the subject or legally acceptable representative.

If a potential subject is illiterate or visually impaired and does not have a legally acceptable representative, the investigator must provide an impartial witness to read the informed consent form to the subject and must allow for questions. Thereafter, both the subject or legally acceptable representative and the witness must sign the informed consent form to attest that informed consent was freely given and understood.

## 11.2 Institutional Review Board

A copy of the protocol, proposed informed consent form, other written subject information, and any proposed advertising material including the information letters must be submitted to the IRB for written approval. A copy of the written approval of the protocol, informed consent form, and advertising material must be received by the sponsor before recruitment of subjects into the study and shipment of investigational product.

The investigator must submit and, where necessary, obtain approval from the IRB for all subsequent changes to the above-named documents. The investigator should notify the IRB of important deviations from the protocol or serious adverse events occurring at the site and other adverse event reports received from the sponsor, in accordance with IRB procedures.

The investigator is responsible for obtaining IRB approval/renewal throughout the duration of the study at the frequency specified by the IRB. Copies of the investigator's reports and the IRB's written continuance of approval must be sent to the sponsor.

## 11.3 Pre-Study Documentation Requirements

The investigator is responsible for forwarding the following documents to the sponsor for review before study initiation from the sponsor can occur:

- Signed and dated protocol signature page (Investigator's Agreement).
- Copy of approved informed consent form and assent form (for phase II).
- Copy of the IRB approval of the protocol, information letter, consent form, and assent form.
- Up-to-date curricula vitae of principal investigator and all co/subinvestigators.
- The IRB composition and/or written statement that IRB is in compliance with regulations.
- Laboratory normal ranges and documentation of laboratory certification (or equivalent).
- Current subject/investigator indemnity insurance.
- Signed study contract.
- Completed FDA form 1572. Laboratories providing primary and secondary endpoint data and any central laboratories for the study must be listed on the form.
- For studies covered under 21 CFR Part 54.2(e), "Financial Disclosure," completed Financial Disclosure statements for the principal investigator, all sub-investigators, and their spouses (legal partners) and dependent children.

## 11.4 Subject Confidentiality

The investigator must take all reasonable measures to ensure that the subject's confidentiality is maintained. On the case report forms or other documents submitted to the study sponsor and those working with the study sponsor, subjects should be identified by their initials and a subject study number only. Documents that are not for submission to the study sponsor and those working with the study sponsor should be kept in strict confidence by the Investigator.

In compliance with Federal regulations/ICH GCP Guidelines, the Investigator and Institution shall permit authorized representatives of the sponsor and companies that work with the sponsor, of the regulatory agency(s), and the IRB direct access to review the subject's original medical records for verification of study-related procedures and data. Direct access includes examining, analyzing, verifying, and reproducing any records and reports that are important to the evaluation of the study. The investigator is obligated to inform and obtain the consent of the subject to permit such named representatives to have access to his/her study-related records without violating the confidentiality of the subject.

## 12 Administrative and Legal Obligations

### 12.1 Protocol Amendments and Study Termination

Protocol amendments must be made only with the prior approval of the sponsor. Agreement from the sponsor must be obtained for all protocol amendments and amendments to the informed consent document. The IRB must be informed of all amendments and give approval for any amendments likely to affect the safety of the subjects or the conduct of the trial. The investigator must send a copy of the approval letter from the IRB to the sponsor.

The sponsor reserves the right to terminate the study, according to the study contract. The investigator should notify the IRB in writing of the trial's completion or early termination and send a copy of the notification to the sponsor.

### 12.2 Study Documentation and Storage

#### 12.2.1 Delegation Log

The investigator should maintain a list of appropriately qualified persons to whom he/she has delegated trial duties. All persons authorized to make entries and/or corrections on case report forms are included on the Delegation of Authority Form.

#### 12.2.2 Source Documents

Source documents are original documents, data, and records from which the subject's case report form data are obtained. These include but are not limited to hospital records, clinical and office charts, laboratory and pharmacy records, diaries, microfiches, radiographs, and correspondence.

#### 12.2.3 Study File

The investigator and study staff are responsible for maintaining a comprehensive and centralized filing system of all study-related (essential) documentation, in a complete, accurate, and legible manner, suitable for inspection at any time by representatives from the sponsor, companies that work for and with the sponsor, and/or applicable regulatory authorities. Elements should include:

- Subject files containing completed case report forms, informed consents, and supporting copies of source documentation.
- Study files containing the protocol with all amendments, investigator's brochure, copies of pre-study documentation, and all correspondence to and from the IRB and the sponsor.
- Proof of receipt, Investigational Product Accountability Record, Return of Investigational Product for Destruction, Final Investigational Product Reconciliation Statement, and all drug-related correspondence.

In addition, all original source documents supporting entries in the case report forms must be maintained and be readily available.

No study document should be destroyed, moved to another location, or assigned to another party without prior written consent of the sponsor.

## **12.3 Study Monitoring and Data Collection**

The sponsor monitor is responsible for inspecting the case report forms at regular intervals to verify adherence to the protocol; completeness, accuracy, and consistency of the data; and adherence to local regulations on the conduct of clinical research. The monitor should have access to subject medical records and other study-related records needed to verify the entries on the case report forms.

The Investigator agrees to cooperate with the monitor to ensure that any problems detected in the course of these monitoring visits, including delays in completing case report forms, are timely resolved.

## **12.4 Publication Policy**

The information provided in support of or generated as a result of this study is confidential. Any use or reproduction thereof, including but not limited to publications or presentations by the Investigator or his associates, must be submitted to the Sponsor for review and approval prior to publication or presentation in any form. All publications must acknowledge the sponsorship.

## 14 Appendix 1 – KB103 Administration and Removal Instructions

### At-Home Administration Instructions

1. Open the compounding, dressing, cleaning and handling kits.
2. Put on the gloves provided with the cleaning and handling kit.
3. You will receive two KB103 vials for each wound to be treated. The vials are shipped on dry ice and stored in an ultra-low temperature freezer at the patient's home. Open the ultra-low temperature freezer and remove four KB103 vials. Inspect the vials for signs of leakage. If leakage as occurred, take a picture of the leakage and dispose of the vial in the provided red biohazard bag.
4. Place the KB103 vials on the blue towel provided in the cleaning and handling kit and let them sit for 20 to 30 minutes to allow the KB103 to warm to room temperature. **Do not let the vials sit for more than 40 minutes prior to use.**
5. The study team will tell you which of the wounds should be given KB103. If you are unsure, contact your study doctor or study coordinator.
6. Unpackage Mepitel One, Mepiform, Vaseline, and Kerlix Gauze dressings that were provided with the dressing kit and place them nearby. Prepare the wound for KB103 administration by unbandaging the area. Cut a hole in Mepitel One to the size of the wound to be treated and place the cut Mepitel on the patient's skin around the wound surface.
7. To compound KB103 with the gel, take one syringe and attached an 18G needle to it. Open a vial of KB103 and draw the product entirely into the syringe (each vial contains 200uL of KB103). Repeat the same procedure to draw the same volume of gel into a second syringe.
8. Activate safety cover of the needles and removes needles from syringes. Discard the needles in the sharp needle's container.
9. Join the two syringes using the guarded Luer lock connector.
10. To mix KB103 and gel (1:1 dilution), place the syringes in a vertical position and keep the syringe containing KB103 on top. Slowly dispense the syringe containing KB103 while drawing on the syringe containing the gel until all KB103 is mixed with the gel. Invert the syringes and repeat this operation twice.

11. Disconnect the syringes, keep the syringe containing the compounded product and apply directly to the patient's skin depressing the syringe plunger very slowly to cover the surface of the wound with KB103. Ensure that the KB103 is contained to the wound without any spillage.  

12. If necessary, open a new syringe, connect the spreader and use it to spread the product on the patient's skin.
  - a. Any spillage on hard surfaces should be immediately wiped up with the provided 10% bleach wipes, and any used wipes should be placed in the provided biohazard container.
  - b. If KB103 spills on an absorbent material such as carpet, while wearing gloves, use a paper towel to absorb any visible KB103. Discard the towel. Spray with Lysol and use a provided 10% bleach wipe to vigorously blot the area.
13. Let the KB103 sit for 5 minutes prior to placing any covering over the wound. Keep the area clean and do not touch the wound during the 5-minute period.
14. After applying KB103, remove the gloves, discard them in the biohazard container, and put on a new pair of gloves.
15. Cover the wound using the non-adherent side of Mepiform on above the wound and then cut to the full size of Mepitel dressings.  

16. Thoroughly wrap the dressing in Vaseline Kerlix Gauze and further dress as normally done.
17. All used materials are to be discarded into a biohazard container. Prior to disposal, thoroughly spray the material (bandages, gloves, syringe, etc) with the provided Lysol spray. Store the biohazard container in a safe place out of reach of pets and children until the day of bandage removal and dressing change.
18. Leave KB103 on the wound for at least 24 to 72 hours.

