## 6      **Investigational Product**

Subjects are administered topical KB103 to one or two wound areas, and topical placebo to a second wound area. Wound areas have a surface area of up to 50 cm^2.

During Cycles 1 and 2, topical KB103 and placebo are administered every two to three days to coincide with bandage changes. Administrations continue until the wound closes, a stopping criterion occurs or at the discretion of the Investigator, not to exceed 3 months per cycle. After the first administration of each cycle, administrations can be administered at home by a trained caretaker at the discretion of the Investigator. These are referred to as "At-Home Topical Administrations" below. During visits to the Investigative site, KB103 may be administered topically by the Investigator. KB103 is prepared according to the pharmacy manual prior to administration.

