### **6.2      Dose Level**

Each topical KB103 dose is 6e8 PFU per wound area per day.

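### The at-home sheet in Appendix 1 allots vials per wound, fixes removal at four and describes drawing one, so it does not match the per-area dose in Section 6.2

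*Protocol*

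**What the plan says.** Protocol Section 6.2 gives the dose by area: "Each topical KB103 dose is 6e8 PFU per wound area per day". Section 6 allows the number of areas to vary: "Subjects are administered topical KB103 to one or two wound areas". Section 6.3 lets an area contain one wound or several, and Section 6.4 restricts KB103 to occasions when a target wound is open.

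The at-home sheet in Appendix 1 counts differently:

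- Step 3, allotment: "You will receive two KB103 vials for each wound to be treated".
- Step 3, removal: "Open the ultra-low temperature freezer and remove four KB103 vials".
- Step 5, after the vials have been taken out and thawed: "The study team will tell you which of the wounds should be given KB103".
- Step 6, dressing: "Cut a hole in Mepitel One to the size of the wound to be treated".
- Step 7, KB103: "Open a vial of KB103 and draw the product entirely into the syringe (each vial contains 200uL of KB103").
- Step 7, gel: "Repeat the same procedure to draw the same volume of gel into a second syringe".

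No step says to draw a second vial, or to repeat the preparation for a second area. SAP Section 3 describes the version 4.0 dose per area in its text, but its table entry for that version is per wound. Neither document states the PFU content of a clinical vial.

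**The concern.** A caretaker may give every at-home dose after the first of each cycle by following this sheet. It should therefore lead from what is due that day to the number of vials for each area. It does not. The allotment is per wound, the removal count is a constant, and the drawing step names one vial. Section 6.2 uses a fourth basis, PFU per area, and nothing on the sheet links it to vials.

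The stake is whether the amount applied at home is the stated one and is the same from area to area. Section 1.6 says that version 4.0 is meant to show how long treatment is needed before Phase 3, and that is easier to interpret when the dose per area is constant. The compliance measure in SAP Section 7.3 counts doses received against doses expected, so it would not reveal a wrong amount within a dose.

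**Working it through.** **Inputs.** Dose: 6e8 PFU per area per day (Section 6.2). Allotment: 2 vials per wound (Appendix 1, step 3), which I take to be per dosing day. Removal: 4 vials (step 3). Vial volume: 200 uL = 0.2 mL (step 7). KB103 areas: 1 or 2 (Sections 6 and 6.3). Wounds per area: 1 or more (Section 6.3). PFU per clinical vial: not given.

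**1. Removal count if wound means wound area.** Vials needed = 2 × areas due.

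| Areas due | Needed | 4 − needed |
|---|---|---|
| 1 | 2 | 2 surplus |
| 2 | 4 | exact |

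The need never exceeds four on this reading.

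**2. Removal count if wound is literal.** Vials needed = 2 × wounds due, over all KB103 areas.

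| Wounds due | Needed | 4 − needed |
|---|---|---|
| 1 | 2 | 2 surplus |
| 2 | 4 | exact |
| 3 | 6 | 2 short |
| 4 | 8 | 4 short |

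KB103 volume per area = wounds × 2 × 200 uL. That is 400, 800 or 1,200 uL for 1, 2 or 3 wounds, a ratio of 1:2:3 against one fixed per-area dose. Two wounds in a single area also need four vials, but all four then go on that area. So four fits both the allotment and a constant two vials per area only when two single-wound areas are due.

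**3. Volume drawn.** Allotment: 2 × 200 = 400 uL of KB103. Step 7 as written: 1 × 200 = 200 uL. Ratio: 200/400 = 0.5. With equal gel, the mixture is 400 uL rather than 800 uL. If step 7 is meant for each vial in turn, the ratio is 1, but the text does not say so.

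**4. Can the 6e8 PFU be reproduced?** Dose per area = vials × 0.2 mL × titer. The clinical titer is missing, so the stated dose can be neither reproduced nor contradicted. The formula shows only what the sponsor must confirm:

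- two vials per area give 6e8 PFU if the titer is 6e8/0.4 = 1.5e9 PFU/mL, or 3e8 PFU per vial;
- one vial per area gives it if the titer is 6e8/0.2 = 3e9 PFU/mL, or 6e8 PFU per vial.

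**5. Exposure to the sheet.** Taking 3 months as 90 days, dosing every 2 to 3 days gives at most 90/3 = 30 to 90/2 = 45 dosing days per cycle, fewer if the wound closes. Some of these are on site.

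**The case against.** The strongest reply is that wound is this protocol's shorthand for wound area. The intent-to-treat definition in Section 10.3.2 explains a paired assessment of the target wound area as one KB103 and one placebo target wound. Section 10.5.3 compares target wounds although selection is by area. SAP Section 3 describes the same version 4.0 dose both per area and per wound. The dressing sentence in step 6, which seems to point to an individual wound, also appears in the on-site procedure in Section 6.4, where the per-area dose applies, so it does not settle the unit. This reply largely stands. The shortages and the 1:2:3 ratio arise only on the literal reading, and the documents do not establish that reading.

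Step 7 can likewise be read as an instruction for each vial, and surplus thawed vials are not an overdose when the same step allots two per wound.

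There are also safeguards. Sections 5.4 and 5.6 put the first dose of each cycle on site. Section 6.1 requires documented training and has the investigator make remote dosing decisions from images. Section 6 refers preparation to the pharmacy manual, step 5 tells a caretaker who is unsure to call, and Section 12.2.3 requires product accountability records. These lower the risk. They do not make the sheet agree with itself: on the shorthand reading four is still wrong when one area is due, and on the per-vial reading step 7 still gives no number of vials per area.

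A reader might go further and infer that subjects received half, double or some other multiple of 6e8 PFU. The documents do not support that. PFU per vial is not stated. The only titer given, 3.4e9 pfu/mL in Section 1.4, belongs to a small-scale in-house stock and cannot be carried over to the clinical vials.

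**Conclusion.** The mismatch between Appendix 1 and Section 6.2 is real and holds in this limited form. The removal count is fixed although the number of areas due is not: it is two vials too many when one single-wound area is due, on either reading of wound. The drawing step, taken literally, uses half the allotted volume. A product amount that rises with the number of wounds is a further consequence only if wound is literal.

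The volume results assume that the two-vial allotment is per dosing day. They say nothing about PFU, and no dosing error is shown. The missing vial content is a limit of the documents available here, not proof of a gap in the trial's files. This version plans three subjects, with training and a route for questions, so the point ranks between minor and should-fix.

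**What to change.** - **Appendix 1, step 3.** Allot vials to each KB103 wound area rather than each wound. Replace the fixed four with the sponsor-confirmed number of vials for each KB103 wound area due today: two, if two are confirmed to equal 6e8 PFU.
- **Appendix 1, step 7.** Say to draw all the vials for that area, mix them with an equal volume of gel, apply the total across the open wounds in the area, and repeat for a second area if one is due.
- **SAP Section 3, version 4.0 row.** Change the dose entry to 6e8 PFU/wound area/day.
- **Optional.** Move step 5 ahead of the removal and thawing of vials.

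The cost is a short edit to the caretaker sheet, sponsor confirmation of the vial content, one SAP table entry and a retraining note. Design, sample size and visits do not change.
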